5.0 Inclusion and Exclusion Criteria/ Study Population

Subjects (male and female), ages 18-85, will be screened and recruited for the study 6-60 months following stroke. The pool of post-stroke candidates for the study will be recruited through the extensive recruiting mechanisms at the local VAMC as well as the Clinical and Translation Tools and Resources CTTR core at MUSC. All participants will have had a new ischemic stroke.

Inclusion criteria will be: 1) age 18-85; 2) stroke at least 6 months prior, 3) residual paresis in the lower extremity (Fugl-Meyer LE motor score <34); 4) ability to walk without assistance and without an AFO during testing and training at speeds ranging from 0.2-0.8 m/s; 5) no antidepressant medications or no change in doses of psychotropic medication for at least 4 weeks prior to the study (6 weeks if newly initiated medication); 6) HRSD question #9 regarding suicide <2; and 7) provision of informed consent. In addition, depressed subjects will screen for probable major depressive disorder (PHQ-9 > 10) and be diagnosed using the Structured Clinical Interview for Depression (SCID) according to the Diagnostic and Statistical Manual of Mental Disorders, Fourth Edition (DSM-IV). All subjects who meet criteria for training must complete an exercise tolerance test and be cleared for participation by the study physician.

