Exclusion criteria will be: 1) Unable to ambulate at least 150 feet prior to stroke, or experienced intermittent claudication while walking; 2) history of congestive heart failure, unstable cardiac arrhythmias, hypertrophic cardiomyopathy, severe aortic stenosis, angina or dyspnea at rest or during ADL's; 3) History of COPD or oxygen dependence; 4) Preexisting neurological disorders, dementia or previous stroke; 5) History of major head trauma; 6) Legal blindness or severe visual impairment; 7) history of psychosis or other Axis I disorder that is primary; 8) Life expectancy <1 yr.; 9) Severe arthritis or other problems that limit passive ROM; 10) History of DVT or pulmonary embolism within 6 months; 11) Uncontrolled diabetes with recent weight loss, diabetic coma, or frequent insulin reactions; 12) Severe hypertension with systolic >200 mmHg and diastolic >110 mmHg at rest; 13) attempt of suicide in the last 2 years or at suicidal risk assessed by SCID interview; 14) History of seizures or currently prescribed anti-seizure medications; 15) Current enrollment in a clinical trial to enhance motor recovery; 16) Pregnancy verified by urine pregnancy test.

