Electromyographic assessment: Surface electromyography (sEMG) will be collected using 2cm by 2cm surface recording electrodes and will be placed perpendicular to the orientation of the fibers of the APB muscle belly, on the participant's non-dominant hand. Prior to sEMG placement the site of the APB muscle will be lightly abraded and cleaned with pre-packaged alcohol swabs. All EMG signals will be collected using Spike2 v7.12 software (Cambridge Electronic Design; Cambridge, UK) and will be amplified (x1000) and bandpass- filtered (100-2000 Hz) using a CED 1902 amplifier (Cambridge Electronic Design; Cambridge, UK), and sampled at 5000 Hz using CED Micro 1401-3 data acquisition unit (Cambridge Electronic Design; Cambridge, UK). Data will be saved directly to a network drive for offline analysis. During all stimulation protocols sEMG activity will be continuously monitored in order to ensure that the APB muscle is not voluntarily active.

Exercise Tolerance Testing: Prior to training, a bicycle ergometry protocol modified from the LEAPS trial⁸ will be used to assess exercise tolerance prior to study inclusion. The protocol will be overseen by a physician and will commence with the subject seated quietly for two minutes. Exercise will begin with the subject pedaling at ~60 revolutions per minute (RPM) and 0 Watts (W) of workload, with workload will be increased by ~15 W every 3 minutes. If the pedal cadence drops below 50 RPM, additional reminders will be given. Testing continues until maximal effort is achieved. The test will be terminated prior to achieving maximum effort for predefined symptomatic, clinical, and electrocardiographic criteria. Symptom-related reasons for termination include angina, dyspnea, and fatigue.

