Fatigue is defined as either voluntary exhaustion or inability to maintain a minimum cycling cadence of 40 RPM. Clinical criteria for termination include: 1) Hypertension: $\geq 220/120$ mmHg, or 2) Hypotension: a drop in diastolic blood pressure >20 mmHg, and O2 saturation $<85\%$. Electrocardiogram criteria include: 1) ≥ 1 mm horizontal or down sloping ST segment depression, 2) sustained paroxysmal ventricular tachycardia (>30 beats), and 3) sustained paroxysmal supraventricular tachycardia (>30 beats). If the test is terminated because of electrocardiographic findings, the subject will be managed medically as needed, referred for care, and disapproved for participation. Resting blood pressure and heart rate will be obtained prior to initiation of exercise as well as after the subject has been sitting on the stationary bicycle for 1 minute. During the exercise test, blood pressure readings will be obtained every 3 minutes. Heart rate will be obtained from the 12-lead EKG. Maximal heart rate will be recorded as the highest heart rate achieved during the exercise tolerance test.

Subject monitoring during testing and training: Blood pressure (BP) and heart rate (HR) will be monitored prior to, during, and at completion of each session. Subjects' resting diastolic BP must be <100 mmHg, systolic < 200 mmHg, and heart rate <110 beats/min to begin the testing.⁷⁴ Criteria for termination include subject complaints of shortness of breath, light-headedness, confusion, severe headache, or dyspnea; onset of angina; excessive blood pressure (systolic BP > 200 mm Hg, diastolic BP > 110 mm Hg), or drop in systolic BP > 10 mm Hg and inappropriate bradycardia (drop in heart rate > 15 bpm).

Experimental protocol for walking data collection: At the beginning of the first training session of every other week (bi-weekly), subjects will walk on a 10m. long gait mat (GaitRite) to measure self-selected and fastest comfortable walking speed and other spatiotemporal parameters. Subjects will be permitted a practice trial, and then be asked to complete three trials at each speed. For all trials, subjects will wear their own shoes and be asked to walk without an assistive device or ankle-foot orthosis. A safety harness mounted to the ceiling will protect the subject but will only support their body weight in the case of a loss of balance. A physical therapist will be present for all testing sessions as needed.

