15.0 Risks to Subjects

A licensed physical therapist will be present during all treatment sessions. In addition, during all treadmill walking trials, a safety harness will be worn to provide assistance in the event of loss of balance. The research staff will closely monitor the subject to ensure their comfort. Any adverse events will be recorded and monitored as required by our Institutional Review Board. In the event of an adverse medical event, standard facility emergency procedures will be followed and proper personnel notified. The PI on this proposal is a licensed physical therapist with several years of experience in the development and implementation of exercise interventions. Any adverse events will be recorded and monitored as required by the IRB. On-site medical services will be available in the event of adverse events to the subjects. Subjects will be able to terminate the training or testing sessions at their request at any time without prejudice. Minimization of risk will be accomplished by monitoring vital signs within prescribed criteria for termination of the training session. We will follow the American College of Sports Medicine criteria for terminating an inpatient exercise session which includes: subject complaints of light-headedness, confusion, or dyspnea; onset of angina; excessive blood pressure changes (systolic BP greater than 220 mmHg, diastolic BP greater than 110 mmHg); and inappropriate bradycardia (drop in heart rate >10 beats per minute).

At any point during the study, should a participant complete the HRSD and answer questions indicating very severe depression (>22) or answer any questions on the HRSD or PHQ-9 indicating any suicidal ideation, thoughts, or plan, they will be immediately referred for clinician evaluation. This includes those patients whose symptoms may worsen during the course of the study. A licensed psychiatrist ([name] or one of his colleagues) will be available during all depression assessments if further evaluation is necessary. In the event of an incident during treatment or training that a clinician is not immediately available, the participant will be escorted to the emergency department for further evaluation.

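### Exclusion 12 joins its two resting blood pressure limits with 'and', which makes it looser than the protocol's own limits for starting and stopping a session

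*Combined protocol and SAP*

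**What the plan says.** Five places in the combined protocol and SAP bear on this.

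- **Section 5.0, exclusion 12:** "Severe hypertension with systolic >200 mmHg and diastolic >110 mmHg at rest".
- **Section 5.0, end of the inclusion criteria:** everyone who meets the criteria for training "must complete an exercise tolerance test and be cleared for participation by the study physician".
- **Section 10.0, Exercise Tolerance Testing:** the bicycle test "will be used to assess exercise tolerance prior to study inclusion". "Resting blood pressure and heart rate will be obtained prior to initiation of exercise". The stated stopping limit for high pressure during this test is 220/120 mmHg or above.
- **Section 10.0, Subject monitoring during testing and training:** this gives a start rule, "Subjects' resting diastolic BP must be <100 mmHg, systolic < 200 mmHg, and heart rate <110 beats/min to begin the testing". It also gives stop criteria that include "excessive blood pressure (systolic BP > 200 mm Hg, diastolic BP > 110 mm Hg".
- **Section 15.0:** a second list of stop criteria includes "excessive blood pressure changes (systolic BP greater than 220 mmHg, diastolic BP greater than 110 mmHg".

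**The concern.** Exclusion 12 is the only criterion in Section 5.0 that deals with severe hypertension by number. Joined by 'and', its limits exclude a person only when both are exceeded at rest. Someone whose systolic alone or diastolic alone is far above its limit does not meet it. Section 10.0 uses the same 200 and 110 as items in a stop list, where exceeding either one is the natural trigger. A person could therefore stay clear of the exclusion with a resting reading that is already past a stop limit.

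At stake is whether a safety criterion works on its face. The intervention is high-intensity, maximum-velocity resistance and jump training in stroke survivors. If the written exclusion does not catch isolated severe elevations, screening has to rely on other steps to do so. At worst, someone might be enrolled who then repeatedly cannot start a session.

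**Working it through.** The plan states no figure on this point that could be reproduced. The check is to apply each rule, as written, to readings of systolic S and diastolic D in mmHg.

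**Rules and where they come from**

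- Exclusion 12 as written (Section 5.0): S > 200 and D > 110.
- Exclusion 12 with 'or': S > 200 or D > 110.
- May begin testing (Section 10.0, start rule): S < 200 and D < 100. The heart rate condition is left aside.
- Stop a session (Section 10.0): S > 200 or D > 110. The text separates the limits with a comma; reading either one as sufficient is an assumption, though the natural one for a stop list.
- Stop a session (Section 15.0): S > 220 or D > 110, read the same way.
- Stop the exercise tolerance test (Section 10.0): S ≥ 220 or D ≥ 120, again reading either value as sufficient.

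**Results**

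| Reading | Excluded, 'and' | Excluded, 'or' | May begin testing | Past Section 10.0 stop limit | Past Section 15.0 stop limit | Past exercise test stop limit |
|---|---|---|---|---|---|---|
| 215/95 | no (95 is not > 110) | yes (215 > 200) | no (215 is not < 200) | yes (215 > 200) | no (215 is not > 220) | no |
| 185/115 | no (185 is not > 200) | yes (115 > 110) | no (115 is not < 100) | yes (115 > 110) | yes (115 > 110) | no |
| 205/115 | yes | yes | no | yes | yes | no |
| 150/95 | no | no | yes | no | no | no |

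The first two rows show the gap: neither reading is excluded, both are past a Section 10.0 stop limit, and neither may begin testing. For 185/115 the conflict is with both stop lists. For 215/95 it is with Section 10.0 only, because Section 15.0 puts the systolic limit at 220.

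**What 'or' does in general**

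1. The 'or' rule is the same condition as the Section 10.0 stop rule. No reading can pass it and still be past that limit.
2. Any reading past the Section 15.0 limit has S > 220, hence S > 200, or has D > 110. The 'or' rule therefore covers that list too.
3. A reading that may begin testing has S < 200 and D < 100, so it has neither S > 200 nor D > 110. The 'or' rule removes nobody whose reading would allow testing to begin.

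**Does another rule already exclude these people?** The start rule blocks both example readings on the day. The protocol gives it as a condition for beginning and does not say that failing it, once or repeatedly, ends eligibility. In the exercise test paragraphs, disapproval for participation is stated only for a test ended by electrocardiographic findings, not for one ended by blood pressure.

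**The case against.** The strongest objection is that Section 10.0 already deals with this. The start rule is stricter than the proposed exclusion. It follows directly after the exercise tolerance test paragraphs, refers to testing, and cites an exercise testing guideline. Its natural scope plausibly includes the exercise test. On that reading, a person who stays at 215/95 or 185/115 could not start the test, could not complete it as Section 5.0 requires, and so would not be included. Physician clearance is a further barrier. Item 3 of the working supports this side as well: the amendment would not stop anyone from exercising at a pressure that the protocol now permits.

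Most of this stands, and it rules out two stronger readings that a reader might infer.

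- *That participants would exercise unprotected at these pressures.* The documents do not support this, because the start rule bars both readings.
- *That entry rests on physician judgement alone, with no stated resting limit, and that 220/120 is the only high-pressure limit bearing on the exercise test.* This would require the start rule not to apply to that test, and the text does not say so. Nor does it expressly name the test, so either scope is an inference.

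What the objection does not do is make exclusion 12 correct. Even if the start rule governs the exercise test, it acts as a same-day hold, and exclusion by that route has to be pieced together.

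A second objection is that 'and' is loose drafting. That is plausible: the exercise test criteria join a diastolic drop and low oxygen saturation with 'and' although they look like separate items. But exclusions 1, 3 and 6 use 'or' where either condition suffices, so a screener has reason to take 'and' literally. A slip is a reason to correct the word.

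Third, stop limits and eligibility limits serve different purposes and need not be equal. That is true, but an eligibility limit at rest that is looser than the limit for halting exercise is hard to justify.

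**Conclusion.** The concern holds as a minor safety and consistency correction. Exclusion 12, taken literally, misses every resting reading with only one value above its limit, and so is looser than the start and stop limits in Section 10.0. Other steps would probably keep such a person from exercising at that reading. The defect is in the eligibility wording and is not an unguarded exercise risk.

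The number affected cannot be estimated from the documents and is probably small. Nothing here changes the sample size, power or the HRSD comparison.

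The literal logic of exclusion 12 is certain. The conclusion otherwise rests on two assumptions: that the comma-separated stop limits are meant singly, and that failing the start rule is a hold and not an exclusion, since no exclusion is stated. If the sponsor intends the start rule to cover the exercise test and to exclude those who persistently fail it, the practical gap closes and only the wording needs repair.

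**What to change.** Change exclusion 12 to: severe hypertension, systolic >200 mmHg or diastolic >110 mmHg at rest. State that it applies to the resting reading already taken before the exercise tolerance test, so that it acts before inclusion.

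The cost is a one-word protocol amendment plus that clarification, with no added measurement. The downside is possibly a few more screen failures, all at readings where the Section 10.0 start rule would not let testing begin.

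The exclusion need not be lowered to match the start rule's diastolic limit of 100. A same-day hold stricter than an exclusion is normal, and that choice can be left to the study physician. The differing systolic stop limits (200 in Section 10.0, 220 in Section 15.0) are a separate inconsistency that this change does not resolve; the same amendment could settle them.

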6.0 Number of Subjects

A total of 48 chronic stroke survivors will be accrued locally.

7.0 Setting

Locomotor Energetics and Assessment Laboratory: This 1350 ft² laboratory is a shared resource supported in part by the Department of Health Sciences and Research, and features equipment capable of collecting kinematic, kinetic, electromyographic data during walking. This laboratory is adjacent to a small workshop available for the construction, repair, and alteration of simple mechanical devices.

Locomotor Rehabilitation Laboratory: This laboratory encompasses an 800 ft² space and is also a shared resource. Specialized equipment within the laboratory that is most relevant to the proposed work is a ZeroG mobile body weight support system as well as a Woodway

split-belt treadmill. The focus of this laboratory is on a multi-faceted approach to locomotor recovery after neurological injury, initially targeting stroke.

8.0 Recruitment Methods

Subject recruitment: The pool of candidates for the study will be recruited from rehabilitation programs at the Medical University of South Carolina; the Ralph H. Johnson VAMC; and Charleston area communities. The combination of MUSC Stroke Center and the Ralph H. Johnson provide a unique environment from which to recruit participants for this study and we have on-going collaborative relationships with both entities. The MUSC program holds Joint Commission's Certificate of Distinction for Primary Stroke Centers which recognizes centers that make exceptional efforts to foster better outcomes for stroke care. The Stroke Center research team will assist with recruitment by reviewing patient rosters and potential participants will be given information while inpatient and again when they are seen for follow up in the outpatient clinic. Rack cards and flyers with basic study information and study investigator contact information will be put on display in the MUSC CHP Research Center. Additionally, the rack cards and flyers will be distributed to area rehabilitation clinics.

The MUSC Stroke Center sees over 50 new stroke patients per month and routinely screens all patients for eligibility to our various research studies.

In addition, since the proposed research investigates stroke recovery it will be supported by the Clinical and Translation Tools and Resources (CTTR) Core of the NIH-funded Center of Biomedical Research Excellence (COBRE) in Stroke Recovery at MUSC. The CTTR Core provides subject recruitment resources through a bioinformatics-enabled database registry. Currently (November, 2017) there are 663 post-stroke subjects in our database registry and ongoing recruitment is expected to add 1-3 more subjects each week. Of these, 157 have screened positive for PSD (PHQ-9 > 10), all of whom have agreed to be contacted for participation in research studies. As evidence of our ability to recruit subjects with PSD, we ([name] and [name]) have been successfully recruiting subjects for a trial as part of the South Carolina Center for Stroke Recovery Research. Over the duration of this study (~26 months) we have successfully enrolled subjects with PSD at a rate that would meet the goals for the proposed study. Thus, we are confident that recruitment goals will be met without difficulty.

9.0 Consent Process

Informed consent will be obtained from participants prior to participation. Participants will first be informed of the purpose of the experiments and possible risks. A member of the study staff will then review the Informed Consent form with the potential participant, ensuring they are given adequate time to review the document. The potential participant will be asked if they have any questions about the study, and asked if they agree to participate. The Informed Consent and HIPAA forms will be signed by the participant. Copies of the signed forms will be given to the participant. The consent process will take place in a private room in the MUSC College of Health Professions Building. There will be no set period between informing the prospective participant and obtaining the consent. In every session, participants will be reminded that they may end their participation in the study at any point.

10.0 Study Design / Methods

Subject screening and clinical assessments: After enrollment, participants will be thoroughly evaluated for functional and cognitive impairments as well as physical performance. Descriptive physical performance testing will include the lower extremity Fugl-Meyer Assessment (FMA-LE), Stroke Impact Scale (SIS), Berg Balance Scale (BBS) and the NIH Stroke Scale. The FMA-LE is a 34-point scale assessing lower extremity function through a progression of items examining more complex movements, speed, and coordination. The SIS is a stroke-specific outcome measure that assesses physical function and other dimensions of health-related quality of life: emotion, communication, memory and thinking, and social role function. The physical functioning domain includes strength, hand function, mobility, and activities of daily living.^{71,72,73} The NIH Stroke Scale measures stroke related impairments including level of consciousness, ability to respond to questions, ability to follow simple commands, deviation of gaze, hemianopsia, facial palsy, limb movements, limb ataxia, sensory loss, neglect, dysarthria, and aphasia. In addition, the Folstein Mini-Mental Status will be used as a screen of cognitive function. Specifically, we will use the three-step command item as a primary screen for study eligibility. All screening and clinical assessments will be performed by a staff physical therapist within the Center for Rehabilitation Research in Neurological Conditions who will be blinded to training group assignment.

Clinical Assessments: The proposed assessments are standard to post-stroke intervention trials. Including these assessments strengthens our design by allowing us to make conclusions regarding the effects of our intervention that extend beyond the behavioral measures of walking. We feel that the proposed benefits of our training will be most significant if they are shown to impact behaviors other than that which is targeted as the primary outcome and relate to other domains of function suggested to put individuals post-stroke at risk for disability.

- **Dynamic Gait Index (DGI):** The DGI evaluates the ability to adapt to changes in task demands. The DGI rates performance from 0 (poor) to 3 (excellent) on eight different gait tasks, including even surfaces, changing speeds, head turns in a vertical or horizontal direction, stepping over or around obstacles, and gait with pivot turns, and steps.⁴² The DGI examines complex walking tasks (e.g. accelerating, turning, head turns) and provides valuable information regarding dynamic balance (as opposed to static balance assessed using the BBS) and often reveals deficits that otherwise would not be identified.
- **Step Activity Monitor (SAM):** The SAM is worn on the ankle to quantify daily step activity. The SAM is a microprocessor-driven accelerometer that permits the researcher to count strides and observe activity during predetermined time spans. The SAM is 98%-99% accurate and has a test-retest reliability post-stroke of 0.98.⁴³ The SAM will be worn for two consecutive days at a 6-second epoch, per the LEAPS protocol.⁸ Information about the effects of POWER training on the amount of community stepping are critical as we attempt to generalize any improvements beyond the laboratory.
- **6-Minute Walk Test (6MWT):** Timed walking tests are primarily a measure of functional capacity.⁴⁴ The 6MWT tests populations who present with little functional walking capacity and has been validated against the Rivermead Mobility Index ($r=0.75$) and 10-meter walk time ($r=-0.61$).⁴⁶ The 6MWT has a high intra- and interrater reliability (ICCs = 0.82-0.95).⁴⁵

Assessment of depression severity: The Hamilton Rating Scale for Depression (HRSD) and the Montgomery- Åsberg Depression Rating Scale (MADRS) are the most widely used instruments for obtaining ratings of depressive symptoms. The HRSD samples a broader array of symptoms and is the primary outcome for this project. However, the MADRS is also sensitive to therapeutic change and includes more focus on vegetative symptoms. Thus, we will utilize a single structured interview that contains the questions necessary to complete both the HRSD and MADRS. The order of questions results in a more efficient interview, clustering material of similar content, thereby reducing repetition. Items that require patient observation (e.g., retardation, agitation) or spontaneous patient report (e.g., HRSD mood item) occur towards the end so scores are not contaminated by direct questioning on these topics. Items dealing with somatic symptoms (e.g., sleep) occur before items focusing on psychological state (e.g., guilt, suicide) so as to develop rapport during the earlier part of the interview leading to fuller disclosure of symptoms that are difficult to discuss. Critically, the rater administering the interviews will not be involved with any other aspects of the study. A trained psychiatry practitioner ([name] or one of his colleagues) will assess depression severity bi-weekly. Test-retest reliability for the HRSD is extremely high (0.94; 95% CI 0.89-0.97) and thus appropriate to use for repeated measure of depression severity.⁴¹ Depression will be classified as mild (HRSD = 12-16) or moderate (HRSD ≥ 17) and diagnosed upon enrollment using the Structured Clinical Interview for Depression (SCID) according to the Diagnostic & Statistical Manual of Mental Disorders, 4th Edition (DSM-IV).

Assessment of cortical excitability and neuroplastic potential via PAS: A means of testing “neuroplastic potential”, without dependence on subject motivation and effort (frequently impaired in depression) is via a non- invasive brain stimulation protocol called paired associative stimulation (PAS). PAS uses repeated, timed and paired peripheral nerve stimulation and TMS of the contralateral motor cortex and induces consistent changes in excitability of the motor cortex in healthy subjects as demonstrated by changes in the amplitude of MEPs.

Prior to PAS, all participants will be assessed for potential contraindications to TMS using a safety-screening questionnaire. This screen as well as the PAS assessments will be performed by personnel with experience utilizing this technique in individuals with PSD. Single pulse cortical stimulation will be delivered using a Bi-Stim module magnetic stimulator (The Magstim Company Limited; Whitland, UK) with a figure-of-eight coil (P/N 3190; 70mm outer diameter of each winding; maximal output of 2.2T). We will use a combination of on-line surface electromyography (sEMG) recordings to view peak-to-peak motor evoked potential (MEP) amplitude and a neuro-navigation system to identify the optimal coil position for stimulation of the abductor pollicis brevis (APB) muscle. The neuro-navigation system consists of a stereotaxic passive marker and camera system (Polaris Vicra P6, NDI, Waterloo, Ontario, Canada) and Brainsight software (Rogue Research Inc.; Montreal, Quebec, Canada), which will allow us to track the location of the figure-of-eight coil and ensure consistency during resting motor threshold (RMT) and SI1mV (stimulus intensity necessary to induce a 1-millivolt MEP response) assessments. In order to locate the APB muscle ‘hotspot’ we will use a suprathreshold stimulation intensity on the hand area of the primary motor cortex to elicit MEP’s of the APB muscle. The area on the hand knob of the motor cortex that produces the largest and most consistent MEP’s of the APB muscle will be marked as the ‘hotspot’ using the neuro-navigation system. After locating the participant’s APB muscle ‘hotspot’ we will then assess the participant’s RMT. We define the RMT as the amount of TMS output (expressed in percentage of maximal stimulator output [%MSO]) necessary to induce an

MEP that exceeds or is equivalent to a peak-to-peak amplitude of $50\mu\text{V}$ (.05mV) in 50% of stimulations. To estimate RMT, we will utilize an automated version of a simple adaptive parameter estimation by sequential testing (SA-PEST) procedure developed at MUSC.⁴⁷

Following RMT assessment, we will assess the participant's $\text{SI}_{1\text{mV}}$. The same 'hotspot' location and SA-PEST procedure will be used to determine the participant's $\text{SI}_{1\text{mV}}$, however the SA-PEST program will be set to search for MEP amplitudes of approximately 1-mV. Once established, the $\text{SI}_{1\text{mV}}$ will be used as a primary measure of corticospinal excitability. Using the %MSO of the $\text{SI}_{1\text{mV}}$ we will then collect 20 test MEP's at a rate of 0.25Hz. Once MEP's are collected, participants will be set-up for peripheral nerve stimulation. Stimulation of the median nerve of the non-dominant arm will be delivered via constant current stimulator (DS7A; Digitimer, Hertfordshire, UK). Bipolar electrodes will deliver a $200\mu\text{s}$ square wave pulse at an intensity equal to 300% sensory perceptual threshold. Perceptual threshold will be determined each session and will be defined before any stimulation protocols are commenced. Single pulse TMS will be applied to the APB muscle representation on the contralateral motor cortex 25ms (ISI25) after the delivery of median nerve stimulation. A train/delay generator (Digitimer, Hertfordshire, UK) will trigger paired peripheral nerve stimulation and brain stimulation. A total of 200 paired stimuli will be delivered at rate of 0.25 Hz, resulting in a total stimulation time of ~14 minutes. The 20 test MEP's will be reassessed immediately after PAS, and then every 15 minutes for one hour.

We will utilize the PAS measures at baseline, after 2,4,6,8,10 and 12 weeks of treatment (or control) as well as at the follow-up time point to assess whether the interventions change PAS measured neuroplastic potential. We will use PAS to assess cortical excitability ($\text{SI}_{1\text{mV}}$) as well as neuroplastic potential (represented by mean normalized post-stimulation MEP amplitude). We will compare PAS measures at baseline to after either POWER or control. We will also compare repeated PAS measures in patients with and without PSD (Aim 2) to determine whether PSD inhibits neuroplasticity, and if effective treatments reverse the impaired potential for plasticity.

Electromyographic assessment: Surface electromyography (sEMG) will be collected using 2cm by 2cm surface recording electrodes and will be placed perpendicular to the orientation of the fibers of the APB muscle belly, on the participant's non-dominant hand. Prior to sEMG placement the site of the APB muscle will be lightly abraded and cleaned with pre-packaged alcohol swabs. All EMG signals will be collected using Spike2 v7.12 software (Cambridge Electronic Design; Cambridge, UK) and will be amplified (x1000) and bandpass- filtered (100-2000 Hz) using a CED 1902 amplifier (Cambridge Electronic Design; Cambridge, UK), and sampled at 5000 Hz using CED Micro 1401-3 data acquisition unit (Cambridge Electronic Design; Cambridge, UK). Data will be saved directly to a network drive for offline analysis. During all stimulation protocols sEMG activity will be continuously monitored in order to ensure that the APB muscle is not voluntarily active.

Exercise Tolerance Testing: Prior to training, a bicycle ergometry protocol modified from the LEAPS trial⁸ will be used to assess exercise tolerance prior to study inclusion. The protocol will be overseen by a physician and will commence with the subject seated quietly for two minutes. Exercise will begin with the subject pedaling at ~60 revolutions per minute (RPM) and 0 Watts (W) of workload, with workload will be increased by ~15 W every 3 minutes. If the pedal cadence drops below 50 RPM, additional reminders will be given. Testing continues until maximal effort is achieved. The test will be terminated prior to achieving maximum effort for predefined symptomatic, clinical, and electrocardiographic criteria. Symptom-related reasons for termination include angina, dyspnea, and fatigue.

Fatigue is defined as either voluntary exhaustion or inability to maintain a minimum cycling cadence of 40 RPM. Clinical criteria for termination include: 1) Hypertension: $\geq 220/120$ mmHg, or 2) Hypotension: a drop in diastolic blood pressure >20 mmHg, and O2 saturation $<85\%$. Electrocardiogram criteria include: 1) ≥ 1 mm horizontal or down sloping ST segment depression, 2) sustained paroxysmal ventricular tachycardia (>30 beats), and 3) sustained paroxysmal supraventricular tachycardia (>30 beats). If the test is terminated because of electrocardiographic findings, the subject will be managed medically as needed, referred for care, and disapproved for participation. Resting blood pressure and heart rate will be obtained prior to initiation of exercise as well as after the subject has been sitting on the stationary bicycle for 1 minute. During the exercise test, blood pressure readings will be obtained every 3 minutes. Heart rate will be obtained from the 12-lead EKG. Maximal heart rate will be recorded as the highest heart rate achieved during the exercise tolerance test.

Subject monitoring during testing and training: Blood pressure (BP) and heart rate (HR) will be monitored prior to, during, and at completion of each session. Subjects' resting diastolic BP must be <100 mmHg, systolic < 200 mmHg, and heart rate <110 beats/min to begin the testing.⁷⁴ Criteria for termination include subject complaints of shortness of breath, light-headedness, confusion, severe headache, or dyspnea; onset of angina; excessive blood pressure (systolic BP > 200 mm Hg, diastolic BP > 110 mm Hg), or drop in systolic BP > 10 mm Hg and inappropriate bradycardia (drop in heart rate > 15 bpm).

Experimental protocol for walking data collection: At the beginning of the first training session of every other week (bi-weekly), subjects will walk on a 10m. long gait mat (GaitRite) to measure self-selected and fastest comfortable walking speed and other spatiotemporal parameters. Subjects will be permitted a practice trial, and then be asked to complete three trials at each speed. For all trials, subjects will wear their own shoes and be asked to walk without an assistive device or ankle-foot orthosis. A safety harness mounted to the ceiling will protect the subject but will only support their body weight in the case of a loss of balance. A physical therapist will be present for all testing sessions as needed.

Post-stroke Optimization of Walking using Explosive Resistance (POWER) training: Individuals with chronic post-stroke hemiparesis will undergo training to improve muscle power generation for 12 weeks (3 times/week) that includes both resistive and task-specific elements. Session duration will be ~ 60 minutes (inclusive of rest intervals) although the total time will depend on the amount of rest needed for a given individual. Training will include five distinct resistance activities aimed at improving muscle power-- each previously reported to contribute to improved walking (Table 1). Sit to stand and leg press exercises are elements of programs shown to be effective in improving strength and walking performance in the post- stroke population.⁴⁸ Repeated step-up training using a single riser targets both eccentric and concentric training in both the sagittal and frontal planes. As possible for individual subjects, we will utilize a step height higher than standard community steps (10") to further challenge neuromuscular requirements of the task. Calf raises (i.e. plantar flexion) will be performed on a small step so as to allow for adequate range of motion. In addition, our pilot data demonstrate that jump training, focused on lower extremity muscle power generation, is part of a comprehensive program that improves gait speed in people with post-stroke gait deficits. Sit to stand, step-up and calf raise activities will be performed within the novel overground body-weight support (BWS) environment enabled by the Zero-G (ZeroG, Bioness Inc., Valencia, CA), whether receiving support or not, to provide the maximum safety possible.

During the initial training session, subjects will perform the individual component tasks beginning with least amount of BWS (or highest load) required for successful completion of

the required number of repetitions in order to match the participant's ability to the difficulty of the task.⁴⁹ BWS will be progressively reduced to determine the minimum support necessary to complete each task. Participants will be progressed within each task by decreasing BWS by 5% of body mass (or adding 5% load for leg press) upon successfully meeting the goals for progression (see Table 1). An adjustable weighted vest will be utilized to increase mass by 5% during training once support is not required for successful task completion. Subjects will not be permitted to use assistive devices and physical assistance will not be provided during training.

